3. STUDY OBJECTIVES

3.1 Primary objective

To evaluate which of the protocols in the study (LCD Vs FPP) has the greatest impact on refractory MGD patient's symptoms (OSDI) on a six-month follow-up

3.2 Secondary objective

Clinical Trial Protocol CPDOXY1

Comparison between continuous and pulsed oral doxycycline treatment protocols for refractory meibomian gland dysfunction - 9 months follow-up prospective study

To evaluate which of the protocols in the study (LCD Vs FPP) has a greater effect on patient's signs (NIBUT; TBUT, Oxford scale) on a six-month follow-up

To evaluate which protocol is related to the lower rate of adverse events

4. STUDY DESIGN

4.1 Study Description

This spontaneous, prospective, non-randomized, parallel-group, phase IV study was conducted in compliance with the tenets of the Declaration of Helsinki.

All study participants were fully consented, and written informed consent was obtained.

This study included patients with refractory MGD. Refractory MGD is defined as symptomatic MGD (OSDI > 13 points) despite 2 months of first-line treatment with lacrimal substitutes 3 times per day and meibomian gland expression with warm compresses twice per day.

The study will consist of 3 visits: Visit 1(Baseline - day 0), Visit 2 (day 90 ± 5 - 3rd month), Visit 3 (day 180 ± 5 - 6 month). At each visit, patients will receive an OSDI questionnaire, NIBUT, type I Schirmer test and AS assessment, including TBUT, corneal staining (Oxford scale)

At baseline, eligible patients will be enrolled and treated with the assigned protocol. The investigators will assign the protocol (non-randomized) in a 1:1 ratio.

At Visit 2, NIBUT, TBUT, Oxford scale and OSDI improvement will be evaluated compared with Visit 1. Patients will be carefully asked about their compliance with the treatment. Patients who interrupted the treatment for adverse events or low compliance (<75% of the protocol adherence) will exit the study and be excluded from the analysis.

At Visit 3, the study population will be evaluated as done in Visit 2

The protocols in the study are the following:

- LCD (low-dose continuous protocol) - 50 mg of doxycycline for three months
- FPP (Full-dose pulsed protocol) - 100 mg of doxycycline for the first 15 days of the month for three months.

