5. STUDY ENDPOINTS

5.1 Primary endpoints

The primary endpoint of this study are:

- OSDI
- Number of patients with OSDI improvement > 7 points (clinically significant)

Clinical Trial Protocol CPDOXY1

Comparison between continuous and pulsed oral doxycycline treatment protocols for refractory meibomian gland dysfunction - 9 months follow-up prospective study

For these parameters, the changes occurring in the two groups at each visit vs baseline will be evaluated.

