11.3.1.1 Primary efficacy endpoint

Paired t-test will be used to study OSDI. Chi-square is used to study clinically significant OSDI variation

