11.3.1.2 Secondary efficacy endpoints

Paired t-test will be used to study the secondary variables.

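### The comparison of regimens is open to confounding: investigators assign the regimen without a stated rule, and no stated test adjusts the between-arm contrast for baseline differences

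*Protocol*

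**What the plan says.** Protocol section 4.1 describes "This spontaneous, prospective, non-randomized, parallel-group, phase IV study" and states how patients reach an arm: "The investigators will assign the protocol (non-randomized) in a 1:1 ratio". It mentions no alternation, matching, stratification, concealment or criterion for the choice.

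The objectives compare the regimens. Section 3.1 reads "To evaluate which of the protocols in the study (LCD Vs FPP) has the greatest impact", with OSDI at six months as the measure. Section 3.2 asks the same kind of question about signs and adverse-event rates.

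Section 5.1 has two primary endpoints, OSDI and the number of patients improving by more than 7 points, and adds: "For these parameters, the changes occurring in the two groups at each visit vs baseline will be evaluated".

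Section 11.3.1.1 fixes the primary tests: "Paired t-test will be used to study OSDI. Chi-square is used to study clinically significant OSDI variation". Section 11.3.1.2 says: "Paired t-test will be used to study the secondary variables". Section 11.3.3 compares dropout rates between groups by chi-square. No section mentions covariate adjustment, matching, a propensity score or a check that the arms are comparable at baseline.

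**The concern.** When investigators choose the regimen freely, whatever guides them may also predict the outcome. Symptom severity, expected tolerance and expected adherence are plausible examples. Fixing the group sizes does nothing about this.

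Baseline severity matters most here because the endpoints are changes. Patients with high scores have more room to improve and tend to regress further. An arm that happened to receive more symptomatic patients could look better on mean change and on the responder count with no difference between regimens. Subtracting baseline does not cure this.

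The dropout comparison is exposed in the same way if expected tolerance influences the choice. At stake is whether the study can answer its own primary question.

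**Working it through.** **The Protocol's own figure.** Section 11.2 takes a 1-second change in break-up time, SD 2.3 seconds, one-sided 2.5% and 80% power, and reports 43 patients.

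- Normal approximation for a paired test: n = ((1.960 + 0.842) × 2.3 / 1)² = 41.5, so 42.
- Exact noncentral t: power is 79.5% at 43 and 80.5% at 44.

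The figure reproduces to within one patient. It is for a before-after test on a different variable, so it neither supports nor refutes this point and supplies no OSDI variability.

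**Size of the possible bias.** Suppose there is no true regimen effect and both arms follow the same regression of follow-up OSDI on baseline. If improvement rises by *s* points per point of baseline OSDI and the arms differ by *g* points at baseline, then

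spurious difference in mean change = s × g.

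Both inputs are assumptions:

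| Slope s | Gap g = 5 | Gap g = 10 |
|---|---|---|
| 0.3 | 1.5 | 3.0 |
| 0.5 | 2.5 | 5.0 |

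**Effect on error rate.** A simulation used an assumed OSDI SD of 20, 32 patients per arm, no true effect and 20,000 runs per scenario. With equal SDs at both visits, s = 1 − r, where r is the baseline to follow-up correlation. Rejection rates are at two-sided 5%:

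| Baseline gap | r | Mean spurious difference | Unadjusted test of change | ANCOVA |
|---|---|---|---|---|
| 5 points (0.25 SD) | 0.7 | 1.5 | 6.8% | 5.2% |
| 5 points | 0.5 | 2.6 | 8.2% | 5.1% |
| 5 points | 0.3 | 3.5 | 8.8% | 4.8% |
| 10 points (0.5 SD) | 0.7 | 3.0 | 12.0% | 4.8% |
| 10 points | 0.5 | 5.0 | 16.6% | 4.9% |
| 10 points | 0.3 | 7.0 | 21.3% | 4.6% |

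ANCOVA holds its level here because baseline OSDI is the only confounder in the simulation. It would not do so against reasons for the choice that are not recorded.

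**Responder count.** Section 6.2 admits patients from an OSDI of 13. To improve by more than 7 points, a patient entering at 13 must lose more than 7/13 = 54% of the score. One entering at 40 needs more than 7/40 = 17.5%. The criterion therefore depends on baseline, and an unadjusted chi-square carries any imbalance straight into the result.

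**The case against.** The study openly declares itself non-randomised. It prescribes treatment as in routine practice (section 7.1), and it is unsponsored, with visits paid through the national health system (section 14.5). A declared design choice is not a contradiction, and an SAP that is not shown might add adjustment. This stands in part: lack of randomisation alone is not an error. But allocation is not a matter for an SAP, the Protocol itself names unadjusted primary tests, and nowhere does it limit its comparative question to an association.

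Several stronger readings are tempting, and the documents do not support them:

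- *That the analysis ignores baseline.* It does not. The endpoints are changes from baseline, section 11.2 links the paired t-test to before-after studies, and the responder criterion is an improvement. What is missing is adjustment of the between-arm contrast.
- *That the result is confounded, in a known direction.* Nothing says how investigators choose or which arm would receive sicker patients. An unstated rule such as alternation is also compatible with the text.
- *That the same unmasked investigators assign and assess.* The Protocol is silent on masking and on who performs each test, and OSDI is a patient questionnaire.
- *That the bias can be judged against the 7-point threshold.* That is a responder cut-off for an individual patient, not a between-arm margin.

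The paired t-test is also a within-group test that estimates no between-arm difference. That is a related but separate defect.

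**Conclusion.** The point holds in limited form. The objectives ask which regimen does better, the allocation is discretionary with no stated rule, and no stated test adjusts the comparison between arms. Differences in OSDI change, responders or dropouts would be open to confounding and regression to the mean.

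For slopes of 0.3 to 0.5 and baseline gaps of 5 to 10 points, the spurious difference in mean change is 1.5 to 5 points. Allowing a slope of 0.7 takes the upper end to 7. These figures rest on assumed slopes and gaps and on a common regression line in both arms. The error rates also rest on the assumed SD of 20. The Protocol gives none of these values, so the figures show what could happen and do not estimate what will. The change is worth making; actual imbalance has not been shown.

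**What to change.** In any case:

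1. Make the primary between-arm test an ANCOVA of Visit 3 OSDI on arm with baseline OSDI as covariate.
2. Adjust the responder comparison for baseline OSDI only, for example by logistic regression. More covariates are hard to support: at an assumed 70% response, 65 patients give about 65 × 0.3 = 20 non-responders, and 43 patients about 13.
3. Report baseline characteristics by arm.
4. Word the conclusions, including those on dropouts, as associations, because adjustment cannot remove unrecorded reasons for choosing a regimen.

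These steps change wording and analysis only and use data already collected.

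If enrolment has not begun, replace investigator choice with a computer-generated 1:1 list, concealed from those enrolling. This adds no visits or patients, but it needs an amendment and investigators give up choosing the regimen. Section 4.1 is partly in the past tense, so this option may already be closed. Steps 1 to 4 do not depend on it, except that the associational wording would no longer be required for a randomised comparison.

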8. STUDY ASSESSMENTS/VISITS

8.1 Study visits:

The study comprises three visits: Visit 1 (baseline), Visit 2 (3rd month), and Visit 3 (6th month).

8.2 Study assessments:

At each visit, the following examinations will be performed in both eyes in the following order:

- OSDI questionnaire
- NIBUT
- Schirmer test
- TBUT
- Corneal staining evaluation (Oxford scale)

All above mentioned examinations and all evaluations required by the study are part of the normal clinical practice.

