11. STATISTICAL CONSIDERATION AND ANALYTICAL PLAN

11.1 Definition of study populations

11.1.1 All Patients Analysis Set

This analysis is not ideal for this study. It will be performed as a secondary analysis, but publication will be based on ITT analysis.

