11.1.2 Intent-to-Treat (ITT) Analysis Set

Signs and symptoms will be analyzed using an intent-to-treat approach. In case of missing data, the last observation available will be carried forward. This will be the primary analysis.

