11.1.3 Safety Analysis Set

Safety analysis will evaluate the number of dropouts related to adverse events for each group

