11.3.2 Compliance analysis

Patient that stopped or missed more than 25% of the assumptions (ex more than 28 cp for LCP or more than 14 cp for FPP)

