11.3.3 Safety analysis

Chi-square is used for drop-out rates between groups

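### Section 4.1 drops patients who stop for adverse events or adhere poorly, while section 11.1 makes intent-to-treat the primary analysis; both cannot hold

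*Protocol*

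**What the plan says.** Section 4.1 (Study Description) states that, at Visit 2, anyone having "interrupted the treatment for adverse events or low compliance (<75% of the protocol adherence) will exit the study and be excluded from the analysis". The rule is not limited to any particular analysis set.

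Section 11.1.2 states: "Signs and symptoms will be analyzed using an intent-to-treat approach. In case of missing data, the last observation available will be carried forward". It then names this as the primary analysis. Section 11.1.1 says of the all-patients set: "It will be performed as a secondary analysis, but publication will be based on ITT analysis". No per-protocol set is defined.

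Dropout is also an outcome in this protocol. Section 11.1.3 says "Safety analysis will evaluate the number of dropouts related to adverse events for each group", and section 11.3.3 says "Chi-square is used for drop-out rates between groups".

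For the primary endpoints, section 5.1 says that "the changes occurring in the two groups at each visit vs baseline will be evaluated".

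Section 11.3.2 gives the compliance limit as patients who stopped or "missed more than 25% of the assumptions (ex more than 28 cp for LCP or more than 14 cp for FPP". The sentence ends there and states no consequence.

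**The concern.** A patient who stops early for an adverse event, or who takes less than 75% of the doses, has two incompatible instructions attached. Section 4.1 removes the patient from the study and the analysis. Section 11.1.2 keeps the patient and fills any gap with the last value.

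The primary objective (section 3.1) compares the two regimens on OSDI at six months. Under the section 4.1 rule, that comparison would be made only among patients who tolerated and took their regimen. The protocol itself treats stopping as something that may differ by arm, so the efficacy set would be selected on an outcome. A regimen that more patients cannot take would be judged on those who could, and the result would still carry the intent-to-treat label. Leaving both rules in place also lets the population be chosen after the data are seen.

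If section 11.1.2 governs instead, the forced exit still does harm. It creates Visit 3 gaps that need not exist, and these are then filled with a day-90 or baseline value.

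**Working it through.** **1. The rules side by side**

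| Patient | Section 4.1 | Sections 11.1.1–11.1.2 |
|---|---|---|
| Stops for an adverse event | Leaves study, not analysed | Analysed, last value carried forward |
| Adherence under 75% | Leaves study, not analysed | Analysed, last value carried forward |

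One might read section 4.1 as a per-protocol rule, but the protocol has no such set. The only secondary set named is all patients, which is the opposite. One might also suppose that these patients exit and carrying forward fills the gap, but section 4.1 excludes them from the analysis as well.

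**2. How many patients could be affected**

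Section 11.2 gives 43 patients (paired t-test, change 1 sec, SD 2.3 sec, one-sided 2.5%, power 80%). Normal approximation: (2.3 × (1.960 + 0.842) / 1)² = 41.5. Adding 1.960²/2 = 1.9 for the t-distribution gives 43.4. Exact power is 79.5% at 43 and 80.5% at 44, so the stated figure reproduces within rounding.

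Enrolment is raised to 65 for dropout. The implied allowance is 1 − 43/65 = 33.8%, or 22 patients. It may cover other losses too, and the protocol states no rate. If 10%, 20% or 33.8% were excluded, about 58, 52 or 43 of 65 would be analysed under section 4.1, against 65 under intent-to-treat.

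**3. What exclusion can hide (all inputs assumed)**

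Let adherers gain 15 OSDI points in both arms. Then

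difference hidden = (stop rate B − stop rate A) × (adherer gain − stopper gain).

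| Stopping, A vs B | Stoppers gain 0 | Stoppers gain 7.5 | Stoppers gain 15 | After exclusion |
|---|---|---|---|---|
| 10% vs 30% | 0.20 × 15 = 3.0 | 0.20 × 7.5 = 1.5 | 0 | 0 |
| 10% vs 20% | 0.10 × 15 = 1.5 | 0.10 × 7.5 = 0.75 | 0 | 0 |
| Equal | 0 | 0 | 0 | 0 |

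For the endpoint of more than 7 points' improvement, suppose 70% of adherers and no stoppers respond, with 10% against 30% stopping. All patients: 0.9 × 70% = 63% against 0.7 × 70% = 49%, a difference of 14 percentage points. After exclusion: 70% against 70%.

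The within-arm change moves as well. With stoppers gaining 0, arm B's mean is 0.7 × 15 = 10.5 in all patients and 15 after exclusion.

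**4. The forced exit**

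Treatment lasts three months and Visit 2 is at day 90 ± 5, so no study treatment is scheduled between Visits 2 and 3 in either arm. Exit at Visit 2 therefore loses only the six-month outcome. Carrying forward then assumes no change from day 90, or from baseline if the patient left earlier. The direction of that error is not established.

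**5. The missed-dose counts**

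Section 7.3 gives half a tablet daily, or one tablet on 15 days a month, for three months. With 30-day months that is 90 LCD doses and 45 FPP tablets.

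- 25% missed: 0.25 × 90 = 22.5; 0.25 × 45 = 11.25.
- Counts in section 11.3.2: 28/90 = 14/45 = 31.1% missed, 68.9% taken.
- LCD patients missing 23 to 28 doses (67/90 = 74.4% down to 62/90 = 68.9% taken) fail the 75% rule but pass the count.
- FPP patients missing 12 to 14 tablets (33/45 = 73.3% down to 31/45 = 68.9% taken) do the same.
- If three months is 92 days, 28/92 = 30.4%.
- The unit is not stated. If it is whole tablets, LCD totals 45 and 28/45 = 62.2%. The dose reading fits better: 28 to 14 has the same 2:1 ratio as 90 to 45.

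**The case against.** The strongest reply is that all the sections can be followed literally. Section 11.1.1 sets an all-patients analysis apart from intent-to-treat and makes it secondary, so the protocol may intend its intent-to-treat set to be something less than everyone: apply the section 4.1 exclusion, call the remainder intent-to-treat, and carry values forward for other gaps. This reading works only by giving the intent-to-treat name to a set selected on tolerability and adherence after treatment start, which is the harm described. It does show that section 11.1.1 needs tidying too.

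Section 11.3.1.1 plans a paired t-test for OSDI, which compares visits within patients, whereas the illustration compares arms. That is a fair description of the test, but the illustration follows the stated primary objective, and exclusion also changes the within-arm means.

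The SAP is not shown and may define a per-protocol set. The absence of such a set therefore carries little weight alone. The problem is that the protocol fixes two incompatible rules, and a SAP could follow only one.

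Section 11 says plainly which analysis is primary, so a reader might give it precedence. Even so, section 4.1 would still send patients out before Visit 3.

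Some points stand. The OSDI gains and stop rates are assumed, carrying the last value forward is a declared rule whose error has no known direction, and the LCD count depends on the unit.

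**Conclusion.** The concern holds: the plan is wrong as written and must be corrected. The contradiction between sections 4.1 and 11.1 is textual and depends on no figure.

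The consequence cannot be sized from the protocol. Under the assumptions shown, exclusion hides between 0 and 3.0 OSDI points, or up to 14 percentage points on the responder endpoint. With equal stopping and equal response the bias is nil. The enrolment allowance of 22 of 65 patients indicates that the number affected need not be small.

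The missed-dose counts are a minor, separate inconsistency. They correspond to 31.1% rather than 25% if doses are counted over 30-day months.

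**What to change.** - **Section 4.1:** remove the exit and exclusion clause and recast the sentence, so that stopping and low adherence are recorded and all enrolled patients are still assessed at Visits 2 and 3.
- **Section 11.1:** state that the primary analysis includes everyone in the assigned arm. Add one line defining a secondary per-protocol set by the 75% rule. Revise section 11.1.1, since the all-patients set then becomes redundant.
- **Section 11.3.2:** reconcile the counts with the 25% limit and the section 7.3 schedule, state the unit, and complete the sentence.
- **Optional:** a repeated-measures model in place of carrying the last value forward, or beside it as a sensitivity analysis.

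The cost is a few lines of text and some follow-up of patients who stopped treatment. Section 8.2 says "all evaluations required by the study are part of the normal clinical practice", so the extra visits add little. Sections 11.3.1.1 and 11.3.1.2 need no change for this point. The change concerns data collection and analysis only and sets no treatment rule. It does not remove confounding from non-randomized assignment by the investigators.

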4.2 End of study

The enrollment period will last about 6 months, so the study will end about 6 months after the last patient enrolls.

5. STUDY ENDPOINTS

5.1 Primary endpoints

The primary endpoint of this study are:

- OSDI
- Number of patients with OSDI improvement > 7 points (clinically significant)

Clinical Trial Protocol CPDOXY1

Comparison between continuous and pulsed oral doxycycline treatment protocols for refractory meibomian gland dysfunction - 9 months follow-up prospective study

For these parameters, the changes occurring in the two groups at each visit vs baseline will be evaluated.

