11.2 Sample size

The sample size estimate was based on a test for before-after studies using a paired t-test, defining a 1-sec change in Break-Up Time as clinically relevant and a standard deviation of 2.3 sec. Setting the error to 2.5% (one-tailed), 43 patients would be required, assuming a power of 80%. Assuming drop out, the final enrollment will be 65 patients.

Clinical Trial Protocol CPDOXY1

Comparison between continuous and pulsed oral doxycycline treatment protocols for refractory meibomian gland dysfunction - 9 months follow-up prospective study

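### Two overlapping primary endpoints, each read at month 3 and month 6, with no deciding endpoint or visit for a single between-protocol objective

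*Protocol*

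**What the plan says.** - **Objective (protocol 3.1).** The primary aim is to find which protocol "has the greatest impact on refractory MGD patient's symptoms (OSDI) on a six-month follow-up". This is one between-protocol question on one symptom score, with no direction given.
- **Endpoints (5.1).** Two are listed as primary: OSDI, and the number of patients whose OSDI improves by more than 7 points. The section then says: "For these parameters, the changes occurring in the two groups at each visit vs baseline will be evaluated".
- **Visits (4.1 and 8.1).** There is a baseline visit and two later ones, at about day 90 and day 180. So each visit after baseline means month 3 and month 6.
- **Tests (11.3.1.1).** The whole text is: "Paired t-test will be used to study OSDI. Chi-square is used to study clinically significant OSDI variation". It gives no visit, order, rule for combining the two endpoints, or division of the error rate.
- **Error rate (11.2).** The only one stated, 2.5% one-tailed, belongs to a sample size for a before-after change in Break-Up Time, which is not a primary endpoint.

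**The concern.** Two endpoints at two visits give four between-arm results, and each could be reported as the primary finding. The second endpoint is a dichotomy of the first, so the two overlap, but they need not agree. Nor need month 3 agree with month 6. The protocol has no rule for the case where one result is significant and the others are not.

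Two things are at stake. First, if the result that reaches significance may be taken as the answer, the chance of a false primary claim exceeds the nominal level of each test. Second, even without a false positive, a reader cannot tell in advance which result answers objective 3.1.

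**Working it through.** **1. The plan's own figure.** Section 11.2 uses a 1 s change in Break-Up Time, SD 2.3 s, one-tailed 2.5% and 80% power. The normal formula is n = (SD × (z₀.₉₇₅ + z₀.₈₀) / change)² = (2.3 × (1.960 + 0.842) / 1)² = 41.5, so 42. With the noncentral t, power is 79.5% at 43 patients and 80.5% at 44. The stated 43 is therefore reproduced to within about one patient. It says nothing about OSDI, but it supplies the only error rate in the protocol: 2.5% one-tailed, equal to 5% two-sided. That is the reference level below.

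**2. Number of results.** 2 endpoints × 2 post-baseline visits = 4 between-arm results. If only month 6 counts, there are 2.

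**3. Simple bounds.**
- Four independent tests at 5%: 1 − 0.95⁴ = 18.5%.
- Upper bound by adding the levels: 4 × 5% = 20%.
- Two independent tests: 1 − 0.95² = 9.75%.

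The real tests are positively related, because they share a score and the same patients, so the true rates lie below these figures.

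**4. Simulation with no true difference.**
- From the protocol: 65 patients, 1:1, so 32 versus 33.
- Assumed: comparable arms, normally distributed change scores, a month 3 to month 6 correlation, and the underlying responder rate.
- Tests at each visit: a two-sample t-test on OSDI change and a chi-square on responders, each at two-sided 5%. A claim is made if any one is significant.

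| Correlation between visits | Four results, chi-square uncorrected (responder rate 30–70%) | Four results, continuity-corrected (responder rate 30–60%) |
|---|---|---|
| 0.5 | 13.8–15.0% | 11.0–11.5% |
| 0.7 | 12.9–14.1% | 10.2–10.8% |
| 0.8 | 12.3–13.3% | 9.7–10.1% |

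With the correlation taken from 0 to 0.9, and including a smaller trial of 21 versus 22, the range is about 11 to 17% uncorrected and about 9 to 12.5% corrected. The combined range is roughly 9 to 17%.

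**5. Last observation carried forward (11.1.2).** This makes month 3 and month 6 identical for some patients. With an assumed 30% carried forward and correlation 0.7, the rate is 11.9% uncorrected and 9.6% corrected, which is inside the same range.

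**6. Fewer results.**
- Both endpoints at month 6 only, either one counting: 7.5–8.3% uncorrected, 6.0–6.4% corrected.
- One deciding test, OSDI change at month 6: 4.9–5.1%.

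**7. The paired t-test as named.** A paired test compares visits within an arm. Run in each arm at each visit, it gives 4 paired tests plus 2 chi-squares, 6 in all, with a combined rate of about 17 to 23% when OSDI does not change in either arm. That null is not the one objective 3.1 asks about. A within-arm change in either arm does not show that one protocol does better than the other, so the fix must also replace the test.

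**The case against.** Several objections carry weight.

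- **The size.** A reader might infer a sharp figure, such as 13 to 15% in place of a promised 5%. The documents do not support that. The protocol gives no OSDI mean, SD or between-visit correlation, does not say whether the chi-square is continuity-corrected, and states an error rate only for the Break-Up Time sample size. The 13 to 15% band fits an uncorrected test with correlation about 0.5 to 0.7; other reasonable choices give 9 to 17%.
- **Any one result counting as success.** The protocol never says that one significant result out of four is enough. The rates above are conditional on that use. If 3.1 is taken to limit the primary claim to month 6, about 6 to 8% applies.
- **A contradiction between 3.1 and 5.1.** It is tempting to say the objective fixes month 6 and the endpoints contradict it. But "on a six-month follow-up" can also mean over six months of follow-up, which takes in both visits. On that reading the sections agree, yet four results remain and none decides.
- **A separate analysis plan.** Testing order and error allocation are often left to a SAP, and none is shown here. The point does not rest on that missing detail. The protocol itself labels two endpoints primary and applies both at each visit, and its own paragraph on the primary analysis does not choose between them.
- **Non-random assignment.** Investigators assign treatment (4.1), so a single test does not by itself secure 5%. This is correct. It limits what the fix achieves but is no reason to leave four primary results open.

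The objections remove the single headline figure and the claim of a firm contradiction. The open choice among four results stands.

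**Conclusion.** The point holds as an unresolved choice of deciding endpoint and visit. Followed as written, the plan yields four between-arm primary results for one question. If any of them may be claimed at two-sided 5%, the false-positive rate is roughly 9 to 17%, falling to about 6 to 8% with both endpoints at month 6 only and about 5% with one deciding test. The sizes depend on assumptions from outside the documents, but in every setting examined more than one deciding result puts the rate above 5%. The change should be made; it does not call the conduct of the trial into question.

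**What to change.** In sections 5.1 and 11.3.1.1:

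- Name one primary result: the between-arm difference in OSDI change from baseline to Visit 3 (month 6), with its two-sided level stated.
- Replace the paired t-test for that result with a between-group method, for example ANCOVA on month 6 OSDI adjusted for baseline OSDI, or a two-sample t-test on the change.
- Make the responder count and all Visit 2 results secondary, reported with confidence intervals.

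If the responder count must stay primary, keep both endpoints at month 6 and fix a testing order or an error split in advance; either also holds 5% when the arms are comparable.

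The cost is a few sentences of wording, with no new data or visits. The downside is that the responder count and the month 3 results can no longer be claimed as primary. The change does not address bias from investigator-chosen assignment, which needs its own treatment.
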